10.1.5.2 Evaluation of Non-Target Lesions

Complete Response (CR): Disappearance of all non-target lesions.

Incomplete Response/Stable Disease (SD): Persistence of one or more non-target lesions and/or maintenance of tumor marker level above the normal limits.

Progressive Disease (PD): Appearance of one or more new lesions* (new lesions must be > slice thickness) and/or unequivocal progression of existing non-target lesions.

Unknown (UN): Assessment of non-target lesions cannot be made due to insufficient or unevaluable data. In this case, a concise explanation must be given.

Note: Although a clear progression of "non-target" lesions only is exceptional, in such circumstances, the opinion of the treating physician should prevail and the progression status should be confirmed at a later time by review of the Principal Investigator. Additionally, the cytological confirmation of the neoplastic origin of any effusion that appears or worsens during treatment is mandatory to differentiate between stable and progressive disease.

***Definition of New Lesion:** The finding of a new lesion should be unequivocal (i.e., not due to difference in scanning technique, imaging modality, or findings thought to represent something other than tumor (ex: new bone lesions may be healing or flare of pre-existing lesions). However, a lesion identified on a follow-up scan in an anatomical location that was not scanned at baseline is considered new and will indicate PD. If a new lesion is equivocal (because of small size, etc.), follow-up evaluation will clarify if it truly represents new disease and if PD is confirmed, progression should be declared using the date of the initial scan on which the lesion was discovered.

10.1.6 Duration of Response

Duration of overall response: The duration of overall response is measured from the time measurement criteria are met for CR or PR (whichever is first recorded) until the first date that recurrence or PD is objectively documented, taking as reference for PD the smallest measurements recorded since the treatment started.

Duration of overall complete response: The duration of overall CR is measured from the time measurement criteria are first met for CR until the first date that recurrent disease is objectively documented.

Duration of stable disease: Stable disease is measured from the start of the treatment until the criteria for progression are met, taking as reference the smallest measurements recorded since the treatment started.

10.1.7 Local failure is defined as the presence of biopsy-proven recurrent cancer at the original site of the primary tumor or radiologic scans that demonstrate progression at that site. Local progression-free survival (LPFS) is defined as the duration of time from enrollment to time of local failure or death.

10.1.8 Regional failure is defined as the presence of biopsy-proven recurrent cancer within the head and neck region outside of the area of the primary lesion or radiologic scans that

demonstrate progression at that site. Regional progression-free survival (RPFS) is defined as the duration of time from enrollment to time of regional failure or death.

10.1.9 Disease-free survival is defined as the time between first study treatment and either recurrent disease or death. Recurrent disease includes a local failure, regional failure, or distant metastasis.

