1.3 Secondary Objectives

- To determine the radiologic response rate following the window treatment as determined by RECIST v1.1, and burden of disease measurements for each cohort
- To determine pathologic response rates following window treatment and rates of pathologic downstaging as compared to pre-surgical staging
 - To correlate pathologic response with radiologic response
- To estimate the 1-year disease free and overall survival rates
- To explore immunologic changes in the tumor microenvironment (infiltrating immune populations including T-cells, myeloid derived suppressor cells, NK cells, and expression of immune checkpoints such as PD-1, PD-L1, PD-L2, and others) and correlate those markers with radiologic and pathologic response, as well as changes in circulating immune markers such as T-cell subsets, B-cells, and myeloid cells. We will also explore the ability of radiologic parameters to predict response rates as well as immunologic changes in the tumor microenvironment.

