5.4 Definition of Dose-Limiting Toxicity

Nivolumab, ipilimumab, and the combination of these two agents have been evaluated in prior phase I protocols and are being evaluated specifically in patients with SCCHN. However, although this is not a phase I protocol, the use of these drugs and the combination in the preoperative setting is relatively novel, and therefore we plan to include a safety-run-in to ensure that treatment is well tolerated in this setting. A separate safety run in will be performed for each cohort. As described in detail Section 14, the safety run-in will first be performed in the nivolumab single agent cohort, using the definitions and window period defined in this section. Once the safety run in has completed successfully with single agent nivolumab, patients will be enrolled to the nivolumab/ipilimumab cohort safety run-in.

The DLT window for this study will be the period between the first treatment and the time of surgery. We will also closely monitor toxicities in the post operative period and during adjuvant treatment; however, given the significant variability in surgical procedure and adjuvant treatment and significant toxicities associated with this when administered as SOC, these will not be considered DLTs. Dose-limiting toxicity (DLT) is based on the CTEP Active Version of the NCI Common Terminology Criteria for Adverse Events (CTCAE Version 4.0). A DLT will be defined as follows:

A patient in either cohort that is medically unable to undergo planned surgery because of toxicities deemed to be the result of experimental treatment or where surgery is delayed by >1 month beyond the originally scheduled date.

Other DLTs will be graded according to the National Cancer Institute's CTCAE version 4.0 (http://evs.nci.nih.gov/ftp1/CTCAE/CTCAE_4.03_2010-06-14_QuickReference_8.5x11.pdf). A DLT is any event that: a) occurs during the DLT evaluation period; and b) is possibly, probably, or definitely related to the administration of nivolumab and/or ipilimumab; and c) fulfills any of the following criteria:

1. Any Grade ≥ 3 pneumonitis, neurological event or uveitis.
2. Any Grade 2 pneumonitis, neurological event or uveitis, with the *following exception*:
 - Grade 2 pneumonitis, neurological event or uveitis that downgrade to Grade ≤ 1 within 3 days after onset, whereby maximal supportive care, including systemic corticosteroids, is permitted.
3. Any *other* Grade ≥ 3 toxicity, with the *following exceptions*:

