All patients who initiate protocol therapy will also be evaluated for response using RECIST v1.1, pathologic response at the time of surgery, safety and tolerability, local failure rate, regional failure rate, local and regional progression free-survival and overall survival. PFS and OS will be analyzed using Kaplan–Meier product-limit estimates and will be plotted using Kaplan-Meier plots. PFS is defined as the time from study randomization to disease progression according RECIST 1.1, medical judgment or death due to any cause, whichever occurred first. Patients alive without disease progression are censored at the date of last disease evaluation. The hazard ratio for each time-to-event endpoint will be estimated with 95% confidence intervals derived from the Cox proportional hazard model, but no hypothesis testing will be conducted. Other definitions are provided in section 10.1.

All patients will be evaluable for toxicity from the time of their first treatment with any study agent. Toxicity will be graded according to NCI CTCAE, Version 4.0. Toxicities will be summarized by maximum grade and by treatment arm. Incidence rate of each toxicity will be reported with 95% exact CI.

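### Disease-free survival has no event for cancer that persists without documented progression, so a living patient with unresected or gross residual tumour can count towards the 1-year disease-free rate

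*Combined protocol and SAP*

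**What the plan says.** Section 1.3 lists as a secondary objective: "To estimate the 1-year disease free and overall survival rates". Section 14 names disease-free survival (DFS) among the secondary endpoints and refers to Section 10.1 for its definition.

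Section 10.1.9 gives that definition: "Disease-free survival is defined as the time between first study treatment and either recurrent disease or death". It continues: "Recurrent disease includes a local failure, regional failure, or distant metastasis". Section 10.1.7 defines local failure as "biopsy-proven recurrent cancer at the original site of the primary tumor or radiologic scans that demonstrate progression at that site". Section 10.1.8 gives regional failure the same two routes, biopsy or scan.

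The analysis paragraph of Section 14 sets a broad population: "All patients who initiate protocol therapy will also be evaluated for response using RECIST v1.1". That sentence goes on to several failure and survival endpoints without naming DFS, but no other DFS population is given. Section 14 states a censoring rule for PFS (last disease evaluation) and none for DFS.

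The plan foresees patients who do not reach surgery. The first dose-limiting toxicity in Section 5.4 is a patient "medically unable to undergo planned surgery because of toxicities deemed to be the result of experimental treatment". Under Section 14, one permanent case of this kind closes that cohort, and closes the study if it occurs in the nivolumab cohort.

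**The concern.** A disease-free endpoint normally starts when the patient has been made free of disease, or else treats failure to get there as an event. This definition does neither. It starts at the first dose, when every patient has tumour, and its events describe cancer that comes back, grows or spreads. Cancer that never went away and has not been shown to grow matches none of them.

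At stake is the meaning of the 1-year disease-free rate. Arms are small, so one patient moves the rate visibly. Scoring is also open to disagreement: one analyst might leave such a patient event-free, another might censor the patient, and a third might call a biopsy of persistent tumour recurrent cancer.

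**Working it through.** **1. The plan's own figures.** No target or precision is given for DFS. The only sample-size figures concern volumetric response, and they reproduce. The exact one-sided 90% lower bound is 0.166 at 6 of 20 and 0.127 at 5 of 20, so 6 is the smallest count that clears 15%. The widest exact 80% interval at n = 20 is 0.324, which rounds to the stated 0.32. None of this depends on DFS.

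**2. How 10.1.7 to 10.1.9 score a living patient with tumour in place.**
- Unresected or residual tumour that grows on scan: event (local or regional failure).
- New distant metastasis: event.
- Unresected or residual tumour, stable or partly shrunken, no metastasis: no event.
- Tumour cleared by treatment other than surgery: no event, and rightly so.

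Only the third case is at issue. If the Section 10.1.5.1 threshold were used for progression, the sum of diameters would have to rise 20% from its smallest value, so a partly shrunken tumour would be far from qualifying.

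**3. Chance of detection.** The study calendar schedules radiologic evaluation at screening and before surgery only. Scans after completion of treatment (Section 5.8.3) and the 1-year restaging (calendar footnote m) are optional. Growth may therefore go undocumented.

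**4. Effect per patient.** Inputs from Section 14: 20 per arm, 40 in total.
- 1/20 = 5.0 points in an arm; 1/40 = 2.5 points overall.
- Illustration with an assumed 4 events in 20 and complete follow-up: 16/20 = 80% as written. With 1, 2 or 3 such patients counted as events: 15/20 = 75%, 14/20 = 70%, 13/20 = 65%.
- With an assumed 6 events in 20: 70% as written, then 65%, 60%, 55%.

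**5. If the patient is censored instead.** Take the 4-event illustration with one such patient. Censored before any event, the Kaplan-Meier estimate is 15/19 = 78.9%. Censored after all four, it is 16/20 = 80%. Either way it exceeds the 75% obtained when persistent cancer counts as an event, by 78.9 − 75 = 3.9 to 80 − 75 = 5.0 points.

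**6. Frequency.** The documents give none. Assume a probability p of 1% to 5% that a patient is unresected or left with gross residual disease. The chance of at least one is 1 − (1 − p)^n: 18% to 64% for n = 20 and 33% to 87% for n = 40. That is the chance that such a patient exists. The rate is inflated only if the patient is also alive at 1 year with cancer and no documented progression or metastasis. If 10% to 50% of them are (also assumed), p becomes 0.01 × 0.10 = 0.001 to 0.05 × 0.50 = 0.025. The chance of at least one is then 2% to 40% per arm and 4% to 64% in the trial. Both ranges rest wholly on the assumptions.

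**7. Does the post-treatment restaging fall within the first year?** On schedule, surgery is by week 4, adjuvant treatment starts about 5 to 8 weeks later, and restaging follows its completion by 10 to 16 weeks. The latest case is 4 + 8 + 16 = 28 weeks plus the length of adjuvant treatment, which the documents do not give. Restaging falls within 52 weeks if that length is under 24 weeks.

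**The case against.** **The definition is broader than recurrence in the narrow sense.** Radiologic progression and metastasis count. A reader might infer that DFS ignores every unresected tumour; Sections 10.1.7 to 10.1.9 do not support that. Nor is every unoperated patient miscounted, since one whose cancer clears without surgery is properly disease-free. This confines the point to persistent cancer without documented progression.

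**The drug-toxicity route is capped.** A reader might infer that patients harmed by the drugs would accumulate as successes, or that the definition favours the more toxic arm. Section 14 closes a cohort after one permanent, drug-caused failure to reach surgery, and the documents give no non-resection rate for either arm. One such patient per arm remains possible. Refusal, withdrawal, intercurrent illness, disease found unresectable and incomplete resection are not capped. Entry does require resectable disease and fitness for anaesthesia, which should keep the numbers low.

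**Such a patient might be censored, not counted as disease-free.** This stands, because no DFS censoring rule exists. It does not remove the problem: in the illustration above censoring takes away at most about 1 of the 5 points, and the choice is left to the analyst.

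**The stakes are secondary.** This also stands. DFS does not enter the go/no-go rule, and Section 14 plans no hypothesis test for time-to-event endpoints.

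**Conclusion.** The point holds in a limited form. DFS as written has no event for cancer that persists without documented progression in a patient never resected or left with gross residual disease. Such a patient remains event-free and can count towards the 1-year disease-free rate while cancer is present. The effect is 5 points per patient in an arm of 20 and 2.5 points in 40. This assumes the patient is alive at 1 year, has no documented progression or metastasis, and is followed to that time without being censored.

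How often this will happen cannot be derived from the documents. A reader might take 18% to 64% per arm as the chance that the rate is inflated. That range concerns only whether an unresected or gross-residual patient exists, under an assumed 1% to 5% rate. A reader might also infer that the trial's main conclusion is exposed. It is not: the primary endpoints, the 6-of-20 rule, the sample size and overall survival are unaffected.

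**What to change.** Three additions:

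1. In Section 10.1.9, state that cancer still present at the first restaging exam or scan after completion of all cancer-directed therapy (Section 5.8.3) is a DFS event dated at that assessment, whether or not the patient was operated on. One rule for both groups avoids calling gross residual disease an immediate failure when adjuvant treatment may yet clear it.
2. State the DFS censoring rule: last disease evaluation, as Section 14 already has for PFS.
3. Report, per arm, the number of patients not resected and the number with gross residual disease. This also shows any patient who has not reached the restaging by 1 year.

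The cost is a few sentences, and possibly one case report form item, since no section expressly requires gross residual status to be recorded. The reported 1-year disease-free rate may be slightly lower. Because post-treatment scans are optional, and some patients are followed elsewhere, some cases will rest on the exam or on outside records. An alternative is to restrict DFS to patients rendered disease-free, or to rename it event-free survival with matching events. Either would serve if stated before the data are analysed.

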10.1.10 Response Review

Central review is not going to be performed.

10.2 Other Response Parameters

Pathologic response should be assessed qualitatively and quantitatively (e.g. percent viable cells) [36, 37] when possible. This will take into account immune infiltration with or without tertiary lymph node structures, evidence of tumor death and subsequent tissue repair – these features should be documented and recorded when observed.

Pathologic staging will also be compared with clinical staging performed at study entry.

For patients that have a PET performed before and after treatment, the maximum SUV of the primary lesion and of the most avid nodal disease within the neck should be recorded before and after study therapy.

11. ADVERSE EVENT REPORTING REQUIREMENTS

11.1 Definitions

11.1.1 Adverse Event (AE)

An adverse event (AE) is any undesirable sign, symptom or medical condition or experience that develops or worsens in severity after starting the first dose of study treatment or any procedure specified in the protocol, even if the event is not considered to be related to the study.

Abnormal laboratory values or diagnostic test results constitute adverse events only if they induce clinical signs or symptoms or require treatment or further diagnostic tests.

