5.2.2 On treatment visits

Reasonable effort should be made to conduct study visits on the day scheduled (+/- 3 days).

Any changes from screening clinical evaluation findings that meet the definition of an AE will be recorded on the AE page of the eCRF.

Cycle 1, Day 1

If screening assessments occur within 3 days before start of study treatment, then they may serve as the baseline cycle 1 day 1 visit and screening tests do not need to be repeated. Pharmacy is allowed to follow the DFCI dosing weight practice which is to use the weight from baseline or the previous dose if it has not changed more than $\geq 5\%$.

Draw blood sample for:

- Hematology panel (Table)
- Chemistry panel (Table)
- Mg, LDH, amylase, lipase, LFTs

Record:

- ECOG PS
- Weight
- Vital signs
- Physical exam
- Concomitant medication use

Review all laboratory results before administering study treatment.

Criteria to treat:

- WBC $\geq 2000/\text{ul}$
- ANC $\geq 1500/\text{ul}$
- Hgb $> 9\text{g/dL}$
- Platelets $\geq 100,000/\text{ul}$
- ALT/AST $\leq 3\text{x ULN}$
- Total bilirubin $\leq 1.5\text{ ULN}$ (or 3 in a patient with well documented Gilbert's syndrome)
- Serum creatinine $\leq 1.5\text{ x ULN}$ or creatinine clearance (CrCl) $\geq 40\text{ mL/min}$ (if using the Cockcroft-Gault formula below):

- $\text{Female CrCl} = \frac{(140 - \text{age in years}) \times \text{weight in kg} \times 0.85}{72 \times \text{serum creatinine in mg/dL}}$

- $\text{Male CrCl} = \frac{(140 - \text{age in years}) \times \text{weight in kg} \times 1.00}{72 \times \text{serum creatinine in mg/dL}}$

Every-2-week assessments, day 1 of cycle 2 (within 3 days of treatment):

Draw blood/collect urine sample for:

CONFIDENTIAL

This document is confidential. Do not disclose or use except as authorized.

- Hematology panel
- Chemistry panel
- Mg, LDH, amylase, lipase, TSH (with reflexive Free T4 and Free T3), LFTs

Record:

- ECOG PS
- Weight
- Vital signs
- Physical exam
 - Given the potential difficulty with radiologic measurements in the oral cavity, photo documentation of the tumor size along with bidirectional clinical measurements is strongly encouraged in all patients around the time of cycle 2 treatment
- Concomitant medication use
- AEs or SAEs

Review all laboratory results before administering study treatment.

Criteria to treat:

- WBC \geq 2000/ul
- ANC \geq 1500/ul
- Hgb $>$ 9g/dL
- Platelets \geq 100,000/ul
- ALT/AST \leq 3x ULN

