 - Grade 3 irAEs that downgrade to Grade ≤ 2 within 3 days, or to Grade ≤ 1 or baseline within 14 days after onset, whereby maximal supportive care, including systemic corticosteroids, is permitted.
 - Grade 3 colitis that downgrades to Grade ≤ 2 within 7 days after onset, whereby maximal supportive care, including systemic corticosteroids, is permitted.
 - Grade 3 asymptomatic endocrinopathy, managed with or without systemic corticosteroid therapy and/or hormone replacement therapy.
 - Grade 3 inflammatory reaction attributed to a local antitumor response (e.g., inflammatory reaction at sites of metastatic disease, lymph nodes, etc.).
 - Grade 3 fatigue for ≤ 7 days.
 - Grade 3 infusion-related reaction (first occurrence and in the absence of steroid prophylaxis) that resolves within 6 hours with appropriate clinical management.
 - Liver transaminase elevation ≤ 8 times ULN that downgrades to Grade ≤ 2 (≤ 5 times ULN) within 7 days after onset, whereby maximal supportive care, including systemic corticosteroids, is permitted.
 - Total bilirubin ≤ 5 times ULN that downgrades to Grade ≤ 2 (≤ 3 times ULN) within 7 days after onset, whereby maximal supportive care, including systemic corticosteroids, is permitted.
 - Grade ≥ 3 neutropenia that (1) is not associated with fever or systemic infection, (2) does not require medical intervention, and (3) improves to Grade 2 within 7 days.
 - Grade 3 and 4 lymphopenia.
 - Grade 3 thrombocytopenia that (1) is not associated with clinically significant bleeding, (2) does not require medical intervention, and (3) improves to Grade 2 within 7 days.

CONFIDENTIAL

This document is confidential. Do not disclose or use except as authorized.

- Isolated Grade 3 electrolyte abnormalities that are not associated with clinical signs or symptoms and are reversed with appropriate maximal medical intervention within 3 days.
- Any pre-existing laboratory abnormality that deteriorates to Grade 3/4, but where the increment of deterioration is considered not clinically significant by both investigator and sponsor.

Immune-related AEs (irAEs) are defined as AEs of immune nature (i.e., inflammatory) in the absence of a clear alternative etiology. In the absence of clinical abnormality, repeat laboratory testing will be conducted to confirm significant laboratory findings prior to designation as a DLT.

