6.3.1 Delays in nivolumab administration

Study drug administration should be delayed for the following:

- Any Grade ≥ 2 non-skin, drug-related adverse event, with the following exceptions: Grade 2 drug-related fatigue or laboratory abnormalities do not require a treatment delay.

- Any Grade 3 skin, drug-related adverse event.

- Any Grade 3 drug-related laboratory abnormality, with the following exceptions: Grade 3 amylase or lipase abnormalities that are not associated with symptoms or clinical manifestations of pancreatitis do not require a dose delay.

 - If a subject has a baseline AST, ALT, or total bilirubin that is within normal limits, delay dosing for drug-related Grade ≥ 2 toxicity

 - If a subject has baseline AST, ALT, or total bilirubin within the Grade 1 toxicity range, delay dosing for drug-related Grade ≥ 3 toxicity

- Any adverse event, laboratory abnormality, or intercurrent illness which, in the judgment of the investigator, warrants delaying the dose of study medication.

Note: If any treatment delay would extend the second cycle beyond the planned surgical date, it is suggested that the second cycle be held and the patient proceed to surgery as scheduled or as soon as medically indicated.

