11.2 Procedures for AE and SAE Recording and Reporting

Investigators will assess the occurrence of AEs and SAEs at all participant evaluation time points during the study.

All AEs and SAEs whether reported by the participant, discovered during questioning, directly observed, or detected by physical examination, laboratory test or other means, will be recorded in the participant's medical record and on the appropriate study-specific case report forms.

The descriptions and grading scales found in the CTEP Active Version of the NCI Common Terminology Criteria for Adverse Events (CTCAE version 4.0) will be utilized for AE reporting. The CTEP Active Version of the CTCAE version 4.0 is identified and located on the CTEP website at:

http://ctep.cancer.gov/protocolDevelopment/electronic_applications/ctc.htm.

All appropriate treatment areas should have access to a copy of the CTEP Active Version of CTCAE.

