12.1.2 Data Submission

The schedule for completion and submission of case report forms (paper or electronic) to the ODQ is as follows:

Form	Submission Timeline
Eligibility Checklist	Complete prior to enrollment with ODQ
On Study Form	Within 21 days of enrollment

CONFIDENTIAL

This document is confidential. Do not disclose or use except as authorized.

Baseline Assessment Form	Within 21 days of enrollment
Treatment Form	Within 14 days of the last day of the cycle
Adverse Event Report Form	Within 14 days of the last day of the cycle
Response Assessment Form	Within 14 days of the completion of the cycle required for response evaluation
Off Treatment/Off Study Form	Within 21 days of completing treatment or being taken off study for any reason
Follow up/Survival Form	Within 21 days of the protocol defined follow up visit date or call

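### Section 11.1.1 keeps asymptomatic, untreated, unrepeated Grade 3-4 laboratory values from being adverse events, and Section 14 does not say whether its maximum-grade toxicity table is built from AE records

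*Combined protocol and SAP*

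**What the plan says.** **Definition.** Section 11.1.1 limits laboratory adverse events by clinical consequence: "Abnormal laboratory values or diagnostic test results constitute adverse events only if they induce clinical signs or symptoms or require treatment or further diagnostic tests". Severity grade is not among the qualifying conditions.

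**Recording.** Section 5.2.2 says: "Any changes from screening clinical evaluation findings that meet the definition of an AE will be recorded on the AE page of the eCRF". The recording rule in Section 11.2 covers "All AEs and SAEs whether reported by the participant, discovered during questioning, directly observed, or detected by physical examination, laboratory test or other means", so a laboratory test is a way of detecting an AE, but the finding must first be an AE. The submission schedule in Section 12.1.2 includes an "Adverse Event Report Form" and names no laboratory form.

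**Analysis.** Section 14 grades toxicity by CTCAE version 4.0, summarizes it by maximum grade and arm, and attaches an exact 95% confidence interval to each incidence. It does not restrict this to drug-related events and does not say whether laboratory rows come from AE records or laboratory results.

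**Related rules.** The Section 9 calendar schedules routine bloods, including a CBC with differential, at the pre-surgery time point. Among its exceptions to DLT, Section 5.4 lists "Grade 3 and 4 lymphopenia". It also says: "In the absence of clinical abnormality, repeat laboratory testing will be conducted to confirm significant laboratory findings prior to designation as a DLT". In Section 6.3.1, "Grade 3 amylase or lipase abnormalities that are not associated with symptoms or clinical manifestations of pancreatitis do not require a dose delay".

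**The concern.** A table by maximum CTCAE grade implies that a Grade 3 or 4 value appears because of its grade. The AE definition works on a different principle: a value counts because of what it caused or what was done about it. If AE records feed the table, the two principles meet, and a severe but silent value that nobody acts on drops out.

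What is at stake is the completeness of some laboratory rows in the descriptive safety summary. Safety and tolerability is a primary objective in Section 1.2, and readers of a small preoperative study of checkpoint inhibitors will look at those rows. Section 2.1.2.3 reports that, in an earlier melanoma study of the combination, the most common grade 3 or 4 treatment-related events were raised lipase (13%), AST (13%) and ALT (11%). Doses and schedules differed there and the rates are not split by symptoms, so they do not measure the gap. They do show that laboratory abnormalities are a main part of this combination's toxicity profile.

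**Working it through.** The plan gives no figure to reproduce on this point. The check is first textual, then a short illustration of size.

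**Step 1. Is there a stated route for a value outside the AE definition?**
- Section 5.2.2 sends to the AE page what meets the AE definition.
- Section 11.2 records AEs and SAEs, so it inherits Section 11.1.1.
- Appendix D, Section 3.10 counts all laboratory tests and hematological abnormalities as safety parameters and has toxicities evaluated by NCI criteria. It does not say that each graded value is recorded on a form or enters the table.
- Section 14 is silent on source.

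No section says that a graded value which is asymptomatic, untreated and unrepeated is recorded for the toxicity summary.

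**Step 2. Which values fall in the gap?**
- *Pre-surgery lymphopenia, Grade 3-4.* It is measured in the differential count. After both doses have been given, no study dose remains to be delayed. It is exempt from DLT, so the confirmatory repeat in Section 5.4 is not prompted. Without symptoms, treatment or work-up it is not an AE under Section 11.1.1.
- *Asymptomatic Grade 3 lipase.* It needs no dose delay under Section 6.3.1. Section 5.4 covers an event that "is possibly, probably, or definitely related to the administration of nivolumab and/or ipilimumab". If the value is so judged within the DLT window, it should be repeated, and the repeat can be read as a further diagnostic test, which makes it an AE. It is in the gap only if judged unlikely or unrelated, or if the repeat is not done.

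The affected set is therefore narrow, and lymphopenia is the main member.

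**Step 3. Size per omitted patient.** Inputs: n = 20 per arm (Section 14); exact two-sided 95% interval (Section 14). The counts are assumed, because the documents give no lymphopenia rate.

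Exact (Clopper-Pearson) limits for x of n: lower = 2.5th percentile of Beta(x, n - x + 1), or 0 when x = 0; upper = 97.5th percentile of Beta(x + 1, n - x). For x = 0 the upper limit is 1 - 0.025^(1/20) = 0.168. For x = 1 the lower limit is 1 - 0.975^(1/20) = 0.0013.

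| Patients in the row | Rate | Exact 95% CI |
|---|---|---|
| 0/20 | 0% | 0 to 16.8% |
| 1/20 | 5% | 0.1 to 24.9% |
| 2/20 | 10% | 1.2 to 31.7% |
| 3/20 | 15% | 3.2 to 37.9% |

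Each omitted patient lowers the rate by 1/20 = 5 percentage points. Omitting the only affected patient moves the row from 5% (0.1-24.9%) to 0% (0-16.8%), so the upper limit falls by 24.9 - 16.8 = 8.1 points. Omitting one of two moves it from 10% (1.2-31.7%) to 5% (0.1-24.9%). Omitting all of three moves it from 15% (3.2-37.9%) to 0% (0-16.8%).

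**The case against.** The strongest reply is that the table need not depend on Section 11.1.1. Section 14 speaks of toxicities graded by CTCAE, not of adverse events. Sections 5.3.1.4 and 6.3.1 name laboratory abnormalities beside adverse events as a category of their own. Appendix D, Section 3.10 treats all laboratory tests as safety parameters, and Section 13.4 lists laboratory records among the sources that support case report form entries. A statistician could build the laboratory rows from laboratory data and be within the plan. This stands: omission depends on the unstated source of the table and is not certain.

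The absence of a laboratory form from Section 12.1.2 also proves little. That list has no concomitant-medication form either, although Section 5.5 requires such medication on the case report form. A reader might infer that laboratory results are not collected at all; an incomplete schedule, and an eCRF that is not in the documents, do not support that.

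A reader might also expect sites to record the same value differently, some following Section 11.1.1 literally and others Appendix D. This is possible, but Appendix D gives no recording instruction to follow, so it remains conjecture.

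Finally, filtering laboratory AEs by clinical consequence is a deliberate and workable choice for event reporting. That is a reason to leave the definition alone. It does not tell the analyst where the graded laboratory rows come from.

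**Conclusion.** The point holds in a limited form. Section 11.1.1 excludes by its wording, the recording rules run through it, and no other section provides for a severe value that is asymptomatic, untreated and unrepeated. If the Section 14 table is drawn from AE records, such values are left out and the affected laboratory rows are understated, by 5 percentage points per patient at 20 per arm. The frequency cannot be estimated: the documents give no lymphopenia rate, and their lipase rates are not split by symptoms or treatment.

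A reader might go further and infer that the co-primary safety endpoint or the stopping rules are compromised. The documents do not support that. Section 14 defines the safety endpoint as the number of DLTs, and Section 5.4 sets its own graded criteria for these, including laboratory ones. The main example, lymphopenia, is exempt from DLT by design. The rule of 6 responders in 20 uses no adverse event data. What is affected is part of a descriptive table that carries no test and no decision rule.

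The conclusion rests on one assumption, that AE records are the table's source, which the documents neither state nor rule out.

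**What to change.** State in Section 14, with a matching line in Section 11.2, that laboratory toxicity rows are derived by CTCAE grade from all protocol-scheduled laboratory results after the first dose. At least every Grade 3 or higher value should be recorded for this purpose, whether or not it meets the AE definition in Section 11.1.1.

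Add that recording a value for the table does not make it an adverse event for expedited reporting. This is why the change belongs with the toxicity summary and not in Section 11.1.1: the Section 11.4 table asks for most Grade 4 AEs within 5 calendar days, and widening the definition could bring silent laboratory values under that requirement.

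The blood draws are already scheduled, so no new tests are needed. The cost is one or two sentences, some extra data entry, and a table that lists more Grade 3-4 laboratory abnormalities.
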